8. Age 40 to 75 years
9. Within 5 years of diagnosis of Parkinson's disease

For Genetic Subtype Subjects

10. A confirmed diagnosis of PD plus a genetic diagnosis consistent with PD, specifically PINK1, parkin, LRKK2 or other mitochondrial genetic subtype
11. Age 21 to 75 years

D2. Exclusion Criteria

1. Allergy to EPI-589 or other components of the EPI-589 tablet formulation
2. Use of antioxidant supplements, specifically vitamins E and C beyond the recommended daily allowance
3. Other Parkinsonian disorders
4. MoCA score of <24
5. Revised Hamilton Rating Scale for Depression ≥ 11
6. Parkinsonism due to drugs or toxins
7. Diagnosis of any other clinically significant neurologic disease that will confound the assessment of effect of study drug on disease progression
8. Malignancy within past two years
9. Pregnant or plans to become pregnant or breast feeding

10. History of stroke
11. History of brain surgery
12. Hepatic insufficiency with liver function tests (LFTs) > 3 times upper limit of normal
13. Renal insufficiency as defined by creatinine > 1.5 times normal
14. End stage cardiac failure
15. Participation within past 3 months and for duration of study in a trial of a device, drug or other therapy for PD

Space intentionally left blank

VI. STUDY PROCEDURES

A. Screening Visit

Screening evaluations will be performed within two months of first dose. The Investigator will inform each prospective subject of the nature of the study, explain the potential risks, and must obtain written informed consent from the subject prior to performing any study-related procedures and prior to the administration of study drug. Screening evaluations consist of the following:

1. Assessment of eligibility
2. Medical history, chart review
3. Receipt and review of previous testing including genetic tests
4. Physical examination* including vital signs
5. Height** and weight
6. 12-lead ECG
7. Laboratory assessments for hematology, coagulation, and serum chemistry*** (See Sections [VII.D2.a](#) and [VII.D2.b](#))
8. Urine pregnancy test (women of childbearing potential must have a negative urine pregnancy test; see Section [VII.D2.c](#))
9. MDS-UPDRS
10. MoCA
11. DaTscan (for idiopathic subjects only)
12. Revised Hamilton Rating Scale for Depression
13. SAE assessments
14. Concomitant medications assessment (last 60 days prior to enrollment)

*Breast exam is at screening physical exam only.

** Height is measured at screening visit only.

***Screening values can be used if done within one month of baseline and if completed under fasted conditions

A1. Run-in Assessments

If the subject is eligible for the study following all screening procedures and is still willing to participate in the study, the subject must return to the clinic within one month for Run-in assessments. These will be performed 30 days (\pm 3 days) prior to baseline after eligibility is confirmed and subject is enrolled in the study. Run-in evaluations consist of the following:

1. Fasting blood-based glutathione cycle biomarkers
2. Fasting CNS biomarkers (lumbar puncture)
3. Fasting urine biomarkers
4. Timed motor tests (for subjects on dopamine therapy)
5. AE/SAE assessments
6. Concomitant medications review

B. Treatment Phase

After the Run-in phase, the subject must return to the clinic within 30 days (± 3 days) for baseline assessments. In-clinic study visits are scheduled at Month 1 and Month 3. The Month 2 study assessments can be conducted via telephone. End of treatment assessments will be conducted at the Month 3 study visit. Pharmacokinetic sampling takes place at Month 1 and Month 3. The baseline and all subsequent laboratory assessments should be obtained under fasting conditions.

B1. Baseline Assessments

The following will be assessed or performed at this visit.

1. Physical examination including vital signs
2. Height and weight*
3. 12-Lead ECG*
4. Fasting blood-based GSH cycle biomarkers
5. Fasting urine-based biomarkers
6. Laboratory assessments for hematology, coagulation and serum chemistry*
7. Urine pregnancy test (females of child bearing potential)
8. C-SSRS (Columbia Suicide Severity Rating Scale)
9. MDS-UPDRS
10. NMSS, PDQ-39, EQ-5D
11. BDI, MADRS
12. Timed motor tests (for subjects on dopamine therapy)
13. AE/SAE assessments
14. Concomitant medications review

* Screening results for these assessments may be used if obtained within 1 month of Baseline and if they are completed under fasted conditions. The baseline laboratory assessments should be obtained under fasting conditions.

B2. Study Visit Assessments

- Month 1 Clinic Visit (Day 29 \pm 3 days):

The following will be assessed or performed at the Month 1 clinic visit:

1. Physical examination including vital signs
2. Height and weight
3. 12-lead ECG
4. Laboratory assessments for hematology, coagulation, and serum chemistry*
5. Urine pregnancy test (females of child bearing potential)
6. C-SSRS
7. Fasting blood-based GSH cycle biomarkers
8. Fasting urine-based biomarkers
9. MDS-UPDRS

10. Pharmacokinetics**: a full plasma drug concentration profile will be obtained from the first 10 subjects to complete 1 month of therapy at each site at: Time = 0, and 0.5, 1, 2, 4, 6, 8, and 12 hours after dosing. 12 hour time point may be obtained at 0 hour.

11. AE/SAE assessments

12. Concomitant medications review

* The laboratory assessments should be obtained under fasting conditions.

- Month 2 Visit (Day 57 ± 3 days)

Month 2 assessments can be conducted by telephone and must include review of:

1. AE/SAE assessments
2. Concomitant medication

- Month 3 Clinic Visit (Day 85 ± 3 days)

The following will be assessed or performed at the Month 3 clinic visit:

1. Physical examination including vital signs
2. Height and weight
3. 12-lead ECG
4. Laboratory assessments for hematology, coagulation, and serum chemistry*
5. Urine pregnancy test (females of child bearing potential)
6. C-SSRS
7. Fasting blood-based GSH cycle biomarkers
8. Fasting urine-based biomarkers
9. Fasting CNS biomarkers
10. MDS-UPDRS
13. Pharmacokinetics**: a full plasma drug concentration profile will be obtained from the first 10 subjects to complete 1 month of therapy at each site at: Time = 0, and 0.5, 1, 2, 4, 6, 8, and 12 hours after dosing. 12 hour time point may be obtained at 0 hour.
11. AE/SAE assessments
12. Concomitant medications review
13. MoCA
14. NMSS, PDQ-39, EQ-5D
15. BDI, MADRS
16. Timed motor tests (for subjects on dopamine therapy)

* The laboratory assessments should be obtained under fasting conditions.

B3. Pharmacokinetics**

Plasma concentration samples will be collected from 20 subjects (10 idiopathic and 10 with genetically defined subtypes) at the following time points:

- Month 1 (Day 29 ± 3 days): 0 hour and 0.5, 1, 2, 4, 6, 8, and 12 hours post-dose
- Month 3 (Day 85 ± 3 days): 0 hour and 0.5, 1, 2, 4, 6, 8, and 12 hours post-dose

** 12 hour PK can be obtained at time 0

The pharmacokinetics samples collection will be monitored as subjects are enrolling and sponsor will alert each principal investigator once the required samples for each subtype are obtained.

B4. Early Termination Study Visit

Subjects who terminate from the study after receiving first dose and prior to the completion of all scheduled visits should have the end of treatment visit assessments completed as soon as possible.

C. End of Treatment Visit

End of treatment visit takes place at Month 3 (Day 85 ± 3 days) and includes the assessments listed in Section **VB2** Study Visit Assessments.

Subjects who have an ongoing AE at the time of study completion will be followed for up to 30 days, until the event resolves, or until the Sponsor and the Investigator agree that further follow-up is not medically necessary.

D. Post-Treatment Follow-up

Post-Treatment Follow-up will be at least 10 days and up to 30 days after last dose, with AE/SAE and concomitant medication assessments conducted by telephone. Additional assessments to be determined at Investigator discretion.

E. Unscheduled Visits

If a subject returns to the clinic outside of the normal study visit windows, assessments will be made at the Investigator's discretion. All study relevant unscheduled visit assessments will be recorded in the case report form (CRF) using the supplemental visit CRF pages.

F. Concomitant Medication

Any medication taken by a subject ≤ 60 days prior to enrollment and during the course of the study and the reason for use of the medication will be recorded on the CRF. During screening, each subject will be instructed to report the use of any medication to the Investigator. Subjects

will also be instructed about the importance of not taking any medication throughout the study (including over-the-counter [OTC] medications) without consulting the Investigator.

G. Prohibited Medications

The following are prohibited while the subject is on study treatment:

1. Use of antioxidants, specifically vitamins E and C beyond the recommended daily allowance. However if the subjects are on high doses of Vitamin E and C and are eligible to participate, they are allowed a 2 weeks washout period prior to enrollment
2. Participation 3 months prior to and for the duration of the study in a trial of a device, drug or other therapy for PD

H. Subject Withdrawals

Subjects receive study treatment until treatment discontinuation for one of the reasons listed below. However, subjects may discontinue study treatment or withdraw their consent to participate in the study at any time without prejudice. The following conditions require subject discontinuation from all study treatment:

1. At their own request or at the request of their legally authorized representative
2. If a subject experiences an adverse event that is deemed related to treatment with EPI-589 and in the Investigator's or the Sponsor's medical judgment continuation of treatment would be detrimental to the subject.
3. At the specific request of a regulatory agency for termination of treatment of an individual subject or all subjects under the protocol
4. Subject participation in another clinical study using an investigational agent or investigational medical device
5. Use of prohibited medications such as vitamins E and C beyond the recommended daily allowance.
6. Refusal of sexually active fertile subjects (excluding subjects who have been sterilized) to use medically accepted methods of contraception
7. If a subject becomes pregnant.
8. Significant noncompliance with the protocol in the opinion of the Investigator or the Sponsor

In all cases, the reason for withdrawal must be recorded in the CRF and in the subject's medical records. If the reason is not known, the subject must be followed to establish whether the reason was due to an AE, and, if so, this must be reported in accordance with the procedures in Section [X.B.](#)

Evaluations should be performed on all subjects who participate but do not complete the study according to protocol. Dropouts may be replaced at the request of the Sponsor. The Investigator will make every effort to contact subjects lost to follow-up.

Every effort will be made to follow subjects who have an ongoing AE at the time of withdrawal until the event resolves, or until the Sponsor and the Investigator agree that further follow-up is not medically necessary.

Space intentionally left blank

VII. STUDY ENDPOINTS AND EVALUATIONS

A. Primary Endpoint

To evaluate the effects of EPI-589 on safety as assessed by occurrence of drug-related serious adverse events in subjects with PD.

B. Secondary Endpoints (Efficacy)

1. Fasting blood-based biomarkers
2. Fasting CNS-based biomarkers
3. Fasting urine-based biomarkers

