2. Clinical disease state as assessed by the Movement Disorder Society-sponsored revision of the Unified Parkinson's Disease Rating Scale (MDS-UPDRS)
3. Disease morbidity as assessed by the Non-motor Symptoms Scale (NMSS), PDQ-39 and EQ-5D
4. Cognitive function as assessed by Montreal Cognitive Assessment (MoCA) and
5. Mood as assessed by the Beck Depression Inventory (BDI) and the Montgomery and Asberg Depression rating scale (MADRS)
6. Pharmacokinetics
7. Hematology, blood chemistry, electrocardiogram

Study design	Open-label study with 30-day run-in phase.
Planned number of subjects	Approximately 40 subjects (20 with genetically-defined subtypes of PD and 20 idiopathic PD subjects). (Adaptive design component allows enrollment of up to 20 additional subjects with idiopathic PD to try to achieve a total of 20 subjects that have a biomarker response to EPI-589.)
Study duration	3 months (85 days \pm 3 days) of study treatment preceded by a 1-month baseline parameter run-in period.
Test product, mode of administration, and dose	Test product EPI-589 in a tablet formulation at a strength of 250 mg Mode of Administration Oral with meal Dose EPI-589 500-mg BID (morning and evening dose along with food)
Reference therapy, dose, and mode of administration	None
Safety monitoring	Clinical 
1. Physical exam and vital signs2. Evaluation of adverse events3. 12-lead Electrocardiogram4. Columbia Suicide Severity Rating Scale (C-SSRS)
	Laboratory 
1. Routine serum chemistries2. Routine hematology tests and coagulation tests

Inclusion criteria (all subjects)

1. Hoehn and Yahr stage ≤ 3.0
2. Ambulatory with or without assistance
3. Sexually active fertile subjects and their partners must agree to use medically accepted methods of contraception (e.g., hormonal methods, including oral, subcutaneous, and intrauterine; barrier methods, including [REDACTED] condom, [REDACTED] condom, or diaphragm with spermicidal gel) during the course of the study and for 3 months after the last dose of study treatment.
4. Willingness and ability to comply with study procedures
5. If on medications for PD drugs, then medication regimen must be stable for 60 days prior to enrollment
6. Abstention from use of other investigative or non-approved drugs for the duration of the trial

For Idiopathic Subjects

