EPI-589 was fast absorbed following oral administration in SAD Study EPI589-13-022. The median C_{max} was attained approximately within 1 hour under fasted conditions after dosing. The median T_{max} values were attained in 0.50 to 1.00 hours over the dose range of 50 to 1000 mg under fasted conditions and 3.01 hours at the 500 mg dose level under fed conditions. Mean half-life ranged from 5.55 to 10.7 hours over the dose range of 50 to 1000 mg under fasted conditions and 4.91 hours at the 500 mg dose level under fed conditions. Half-life was independent of the dose levels over the dose range of 50 to 1000 mg under fasted conditions. The rate of EPI-589 absorption, as measured by C_{max} , was decreased by 24.07% under fed conditions at the 500 mg dose level. The extent of absorption as measured by AUCs (AUC_{0-t} or AUC_{0-inf}) was not affected under fed conditions in the 500 mg dose groups.

In MAD study EPI589-14-01, EPI-589 was rapidly absorbed following oral administration and the median C_{max} was attained within 1 hour (0.50 to 0.76 hours) under fasted conditions after single or multiple dosing among these five cohorts. The mean half-life of EPI-589 ranged from 5.64 to 8.47 hours among these five cohorts. In general, the mean values of the time to peak concentration (T_{max}), half-life ($t_{1/2}$), apparent terminal constant (λ_z), accumulation ratio (AR), percent fluctuation (%F) and accumulation index (AI) of EPI-589 were similar among the five cohorts of various ages and smoking status. No significant effects of age or smoking on EPI-589 pharmacokinetics were observed in this study. Dose proportionality existed in the exposures (AUC_{0-tau} , C_{max} , C_{min} and C_{avg}) over the dose range of 250 to 500-mg BID EPI-589 under fasted conditions.

F. Clinical Study

EPI589-15-002: A Phase 2A Safety and Biomarker Study of EPI-589 in in Mitochondrial Subtype and Idiopathic Parkinson's Disease Subjects.

G. Selection of Drugs and Dosages

The study drug in this trial is EPI-589: common chemical name (R)-troloxamide quinone.

Each tablet contains 250 mg of EPI-589. The study dose is 500-mg BID, to be maintained in the absence of treatment-emergent toxicity. EPI-589 tablets must be taken morning and evening with meals.

H. Compliance Statement

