Under an adaptive design strategy, additional subjects (up to 20) may be added to increase the number of biomarker responsive idiopathic PD subjects. Given that the investigational drug targets an enzyme key to glutathione synthesis and that glutathione depletion has been found to be associated with PD, we are seeking to determine the safety and potential biochemical benefit of EPI-589 in PD subjects as assessed by glutathione cycle biomarkers. If we determine that there are a subset of idiopathic PD patients—whether due to disease stage or baseline biomarker profile—who are more likely to be EPI-589 responsive, we will seek to enroll additional numbers of these subjects in the adaptive phase so that we can increase the number of likely biomarker responsive subjects. EPI-589 will be administered for up to 3 months (85 days \pm 3 days) unless discontinued for safety or tolerability issues.

A1. Screening Phase

Suitable candidates for the trial will receive a short overview of the study by the Investigator's staff and, if interested, will undergo Screening. The Investigator will inform each prospective subject of the nature and details of the study, explain the potential risks and must obtain written informed consent from the subject or their legally authorized representative prior to performing any study related procedures.

A2. 30-Day Run-in Phase

Once eligibility is confirmed, the subject will be enrolled in the study and the run-in scans, CNS, blood-based biomarker, urine-based biomarker and clinical measurements will be collected.

A3. Baseline

Baseline assessments, scans, blood-based biomarker, urine biomarker, and clinical measurements will be collected.

A4. Treatment Phase

EPI-589 dosing will start on Day 1. Subjects will self-administer EPI-589 at a dose of 500-mg BID (morning and evening dose along with food).

Blood-based biomarker, urine biomarker, and clinical measurements will be collected at Day 29 (\pm 3 days) and Day 85 (\pm 3 days).

A5. End of Treatment

End of treatment data will be collected at the last study visit Day 85 (\pm 3 days).

AEs reported as ongoing at Day 85 (\pm 3 days) and/or any concomitant medications associated with such events will be followed for up to 30 days, until the event resolves, or until the Sponsor and the Investigator agree that further follow-up is not medically necessary.

A6. Post-Treatment Follow-up

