2. Added the term morning and evening dose to BID	To provide further clarification that dosing is twice daily rather than every 12 hours.
3. Non-clinical studies language	To provide updated information on nonclinical studies.
4. Changed the language under pharmacokinetics (PK) section	To clearly define the expected number of PK blood draws
5. Changed the timed motor test as ON state only (for subjects on dopamine therapy)	To clarify that sites can perform TUG test on subjects in ON state only
6. Dose Limiting Toxicity	To provide clear definition for dose limiting toxicities (DLTs)
7. Administration of clinical assessment	To clarify the primary administrator of the PD assessments for the study
8. Washout period for subjects on high doses of Vitamin E or C	To clarify the need for a 2 week wash out prior to enrollment for subjects on higher doses of vitamin C and E supplements
9. CBC differential as absolute or percentages	For better clarity about recording the values
10. CO ₂ for serum chemistry	CO ₂ is taken and assessed as bicarbonate in most clinical labs. Hence replaced the term Co2 as bicarbonate in the protocol. This is a venous sample.
11. Day 1 first dose language	To clarify that first dose may be taken same day as baseline visit after completing all assessments
12. Changed the height measurement to screening visit only	To clarify that height measurement need not be repeated after screening visit
13. Included breast exam as part of screening physical exam	To capture the findings from breast exam as part of the screening physical exam
14. Removed language in adverse event reporting	To clarify reporting for adverse events
15. Changed the AE language under post-treatment follow up	To clearly define the post treatment follow-up to be at least 10 days after last dose and if there are any ongoing or new AEs noted at month 3, then the follow up will be up to 30 days after last dose

DESCRIPTION OF CHANGES TO THE PROTOCOL

Changes to the protocol by section appear in the table below. Administrative and editorial clarifications, corrections or adjustments may not be individually identified.

In this summary document, ***bold italic*** font indicates additions to existing text, and ~~strikethrough~~ font indicates deleted text. The actual amended protocol does not include bold or strikethrough font to indicate changes.

Protocol Section	Modification

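### Letting the time-0 sample count as the 12-hour PK sample is valid only with 12-hour dosing intervals, which the protocol does not require, so C12 and half-life can be misstated

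*Protocol*

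**What the plan says.** Section VI.B3 calls for samples at "0 hour and 0.5, 1, 2, 4, 6, 8, and 12 hours post-dose" at Month 1 and Month 3, and its footnote adds that "12 hour PK can be obtained at time 0". Footnote c of the Schedule of Assessments (Section II) gives the same permission. So do the PK items of the Month 1 and Month 3 visit lists in Section VI.B2: "12 hour time point may be obtained at 0 hour".

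On dosing, Section III.G says "EPI-589 tablets must be taken morning and evening with meals". The synopsis and Section V.A4 agree. The Amendment 5.0 Summary of Changes (item 2) gives the reason for this wording, which still stands: "To provide further clarification that dosing is twice daily rather than every 12 hours".

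Section VI.B adds, for the visits, "The baseline and all subsequent laboratory assessments should be obtained under fasting conditions". Section IX.D provides a Dosing Diary. Nothing in the protocol fixes the interval before a PK visit, ties the diary to the PK draw, or limits the substitution to subjects who dosed 12 h earlier.

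**The concern.** At time 0 the concentration reflects the previous evening's dose. At 12 h it reflects that morning's dose. The two agree only when the subject is at steady state and successive doses are 12 h apart. The dosing text does not require that spacing, and the stated reason for it says that 12-hour spacing is not meant. The fasting rule makes a longer overnight gap plausible on PK days, because a dose taken with a meal has to follow the fasting collections. The protocol gives no clock times, however, so the length of the gap is inference.

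PK is a secondary objective (Section IV.B) and a listed secondary endpoint (Section VII.B). Section VI.B3 plans profiles from 20 subjects. With late samples only at 6, 8 and 12 h, one mislabelled value has great leverage on the fitted terminal slope. Profiles with a real 12 h draw and profiles with the substituted value would also be pooled without being comparable.

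**Working it through.** The plan states no PK figure to reproduce, so the check is how far C12, half-life and AUC0-12 move when the time-0 value is entered as C12.

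**Inputs from Section III.E.** Half-life 4.91 h (500 mg, fed), up to 8.47 h (longest mean in the multiple-dose study) and up to 10.7 h (longest fasted single-dose mean). Median Tmax 3.01 h fed.

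**Assumptions.**
- The overnight gap G is 10 to 16 h; the daytime interval is 24 − G.
- One compartment with first-order absorption.
- The next evening dose falls after the true 12 h sample.

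**Model.** ke = ln 2 / t½. ka solves ln(ka/ke)/(ka − ke) = 3.01, which gives 0.647, 0.865 and 0.961 per hour for half-lives of 4.91, 8.47 and 10.7 h. The concentration at time t is the sum, over all past doses, of ka/(ka − ke) × [exp(−ke·x) − exp(−ka·x)], where x is the time since each dose. Doses fall at 0, −24, −48 … and at −G, −G−24 … hours. The value at 12 h is then replaced by the value at time 0. Half-life is refitted log-linearly to 6, 8 and 12 h, and AUC0-12 is recomputed by the linear trapezoid rule.

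**Example, t½ 4.91 h, G = 14 h.** True C12 is 0.276 and C0 is 0.228 (arbitrary units): 0.228/0.276 − 1 is about −17.5%. The fitted half-life falls from 5.13 to 4.09 h: 4.09/5.13 − 1 = −20.3%.

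**Error relative to a sample truly drawn at 12 h:**

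| t½ (h) | Gap (h) | C12 | Fitted half-life | AUC0-12 |
|---|---|---|---|---|
| 4.91 | 10 | +21.0% | +33.5% | +1.7% |
| 4.91 | 12 | 0 | 0 | 0 |
| 4.91 | 13 | −9.2% | −11.3% | −0.8% |
| 4.91 | 14 | −17.5% | −20.3% | −1.4% |
| 4.91 | 15 | −25.0% | −27.6% | −2.1% |
| 4.91 | 16 | −31.8% | −33.6% | −2.6% |
| 8.47 | 14 | −7.2% | −14.1% | −0.8% |
| 8.47 | 16 | −13.7% | −24.6% | −1.5% |
| 10.7 | 10 | +4.9% | +15.3% | +0.6% |
| 10.7 | 13 | −2.4% | −6.2% | −0.3% |
| 10.7 | 16 | −9.1% | −20.9% | −1.1% |

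With an assumed fasted Tmax of 0.75 h (the protocol gives 0.50 to 1.00 h), the errors in C12 and half-life are almost the same. At t½ 4.91 h and G = 14 h they are −17.6% and −19.7%.

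**Dropping C12 without replacement.** Fitting only 4, 6 and 8 h in the fed model at t½ 4.91 h returns about 6.0 h, since 6.0/4.91 = 1.22, or 22% too long. Absorption is not complete at 4 h when Tmax is 3.01 h.

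**The case against.** The case for leaving the rule alone has real force. The substitution is optional. The time-0 value is a genuine overnight trough, and only its label as a 12 h value is wrong. PK is secondary, the protocol names no trough, half-life or AUC parameter for this trial, and no dose or stopping decision rests on one. An analysis plan not shown here could use actual elapsed times. Most of this stands, and it limits the consequence. But actual times can be used only if sites record when the preceding dose was taken, and that is a collection matter for the protocol. Even then the sample follows a different dose and meal.

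Four stronger readings are tempting and are not supported:

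- **Simple decay after one dose.** The ratio 2^(−(G − 12)/t½) at t½ 4.91 h and G = 14 to 16 h suggests C12 is 25% to 43% too low. It compares two times after the same dose. The sample replaced is the one after the morning dose under repeated unequal intervals, and carry-over shrinks the error to about 17% to 32%.
- **Exposure made to look safer.** The safety margins in Section III.D1 use Cmax and AUC. Cmax is not touched by the substitution, and AUC0-12 moves by less than 3%.
- **A known direction.** No passage gives meal times, clinic hours or travel. A gap shorter than 12 h reverses the sign.
- **Loss of a steady-state check.** By Day 29, 28 × 24 / 10.7 = 63 half-lives have passed even at the longest mean half-life, so C0 against C12 is not needed to establish steady state.

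**Conclusion.** The point holds as a conflict between the sampling rule and the dosing text. The rule mislabels C12 whenever the preceding interval is not 12 h, and nothing in the protocol detects or prevents that. For assumed gaps of 13 to 16 h and half-lives of 4.91 to 10.7 h, C12 is about 2% to 32% too low and the fitted half-life about 6% to 34% too short. For a 10 h gap, C12 is 5% to 21% too high and half-life about 15% to 33% too long. AUC0-12 is affected only marginally.

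These sizes rest on the assumed gaps, the one-compartment model and the fed Tmax. That the error is zero only at a 12 h interval does not depend on the gap chosen. The primary safety endpoint is unaffected. The change is worth making because it is cheap and has to be made at data collection.

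**What to change.** Reconcile the PK rule with the dosing text in footnote c of Section II, the Month 1 and Month 3 PK items of Section VI.B2, and Section VI.B3:

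- Record the clock time of the dose preceding each PK visit, for example from the Dosing Diary, in a CRF field.
- Report the time-0 value as a pre-dose trough at its actual elapsed time.
- Let it also count as C12 only when that interval is 12 h within a tolerance that the sponsor sets in advance.
- Otherwise use a sample actually drawn at 12 h or leave C12 missing. Where it is missing, do not report half-life from the 4 to 8 h points alone.

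The cost is one CRF field, aligned wording in four places and some profiles without a C12. The change concerns sampling and labelling only and alters no dosing rule. How a real 12 h draw sits relative to the evening dose is not stated, and the sponsor should settle it when reconciling the passages.
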